4. Patients with strength training will activate type II macrophages which are anti-inflammatory and pro-regenerative, tipping the balance away from inflammation towards regeneration when compared to the other treatment groups. Since strength training is likely to initiate signals of muscle regeneration, and since type II macrophages play a key role in this effect, it is possible that increasing the signaling to the muscle for regeneration may also increase the proportion of active type II macrophages which are anti-inflammatory. To test this hypothesis, we will test the proportion of peripheral blood M1/M2 macrophages at baseline, 6 months and 12 months after the initiation of the intervention. Recognizing that immunosuppression may significantly confound this proportion and overall suppress it, we will also test circulating levels of pro-inflammatory cytokines such as C-reactive protein(CRP), IL-6, IL-1, TNF-alpha, homocysteine, adiponectin, leptin, and resistin as well as pro-regenerative cytokines such as TGF-beta and IL-10.

5. We expect patients with strength training will experience less renal dysfunction, decreased hemoglobin A1C, increased peripheral vascular function, decreased fasting blood sugar when compared to the other treatment groups. The rationale for this hypothesis is the finding that muscle mass provides active regulation of glucose and other metabolites. Therefore increasing this may provide improved metabolic function. These laboratory panels are part of the standard transplant follow-up labs and add no cost to the project.

6. Patients with strength training will have an overall improved sense of well-being and energy level compared to those with physical therapy or no treatment. With twice weekly counseling for activity and nutrition, patients will be asked about their general health, mental health and pain intensity using the PROMIS questionnaires.

METHODS

Setting: The study will include 225 patients, to achieve a goal of 180 patients in the GH study group and 45 patients in the control group. Every patient will be followed for 3 years after the start of the intervention. Patients will start the intervention at least 2 months post-transplant; however they can be enrolled prior to transplant.

Main Study Inclusion criteria:

- Successful kidney transplantation (KTx) with primary graft function
- Age between 18 and 65 years

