- Adequate cognitive ability to complete the questionnaires, give consent for the study and follow the physical and diet instructions

Main Study Exclusion criteria:

- transplant of any other organ besides kidney alone or a combination of a kidney/pancreas

- non-ambulatory or significant orthopedic problems
- cardiac/pulmonary disease that contraindicate the physical training
- any contraindication to exercise testing per the American Heart Association
- unable to comply with the training program

Muscle Biopsy Inclusion:

- Age between 18 and 65 years
- Patients who have a brachial–cephalic arteriovenous fistula (AVF) in the elbow or brachial–basilic AVF in the arm
- Exercise Arm- the biopsy will only be performed once, after the 12 month exercise intervention is completed (which will be longer than 1 year post transplant surgery)
- Control Arm- this procedure will be performed once, around one year post transplant surgery (may occur at any time during the study)

Muscle Biopsy Exclusion:

- Patients that do not meet the inclusion criteria

Identifying potential subjects for recruitment:

A waiver for an alteration of consent and waiver of documentation of consent is being requested for review of medical records to identify potential patients for study recruitment and also for a telephone screening process for patients that response to a recruitment flyer. The principal investigator already has access to these records as part of daily care for all patients seen in clinic. This presents no more than minimal risk since this data will be kept confidential.

Moreover, as part of the telephone screening process for patients interested in this study there will be oral consent obtained to start the screening process in order to determine if the patients are eligible to be in the study. If the patients are eligible, they will be schedule for a visit where they will be consented to be in the study.

Randomization: All patients who meet the enrollment criteria will be randomized 4:1 to the GH group or the control group.

- GH group: patients will be treated for 12 months with the GH method (Appendix 1) for one hour twice a week

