Week 42	1 Warm Up Set: 8 – 12 reps. 1 Heavy Set: 8 – 12 reps. Slower Speed.	Moderate/Heavy	2 minutes
Week 43	3 Sets on each exercise of 6, 8, 12 repetitions. Lower weights each set. Medium speed.	Moderate	3 minutes
Week 44	1 set 90 seconds focused on resistance. Medium speed.	Lighter	2 minutes
Week 45	1 Warm Up Set: 8 – 12 reps. 1 Heavy Set: 8 – 12 reps. Slower Speed.	Moderate/Heavy	2 minutes
Week 46	3 Sets on each exercise of 6, 8, 12 repetitions. Lower weights each set. Medium speed.	Moderate	3 minutes
Week 47	1 set 90 seconds focused on resistance. Medium speed.	Lighter	2 minutes
Week 48	1 Warm Up Set: 8 – 12 reps. 1 Heavy Set: 8 – 12 reps. Slower Speed.	Moderate/Heavy	2 minutes
Week 49	3 Sets on each exercise of 6, 8, 12 repetitions. Lower weights each set. Medium speed.	Moderate	3 minutes
Week 50	1 set 90 seconds focused on resistance. Medium speed.	Lighter	2 minutes
Week 51	1 Warm Up Set 8 reps 1 Heavy Set 8 reps	Heavy	3 minutes
Week 52	Cardio Exercises. 10 exercises in a set. 2 Sets.	Moderate	3 minutes

GH Method: List of Strength/Resistance Exercises

MEN

WOMEN

Exercise

Exercise

Chest: Smith Bench Press/Incline	Glutes: Abductor
Glutes: Abductor	Biceps: Cable Easy Curl / Free Bar
Biceps: Cable Easy Curl/Free Bar	Quads: Leg Extension
Quads: Leg Extension	Chest: Smith Press
Calves: Calf Machine	Abs: Decline
Biceps: Preacher	Quads: Leg Press
Quads: Leg Press	Back: Pull Down Behind
Quads: Leg Extension	Hamstring: Machine
Abs: Decline	Shoulders: Dumbbell Press / Smith Press
Back: Pull Down Behind	Triceps: Push Down / Kick Back / Rope Pull down
Hamstring: Curl Machine	Back: Low Roll
Shoulders: Dumbbell Press / Smith Press	Abs: Sit-Ups
Back: Low Roll	Shoulders: Side Raise with Dumbbells
Hamstring: Good Morning with Dumbbell/ 1 Leg Hamstring Curl	Triceps: Close Grip
Shoulders: Side Rise with Dumbbells	Hamstring: Good Morning with Dumbbells/1 Leg Hamstring
Triceps: Push Down / Kick Back	Triceps: Push Down / Kick Back
Abs: Sit Ups	Abs: Sit Ups
Triceps: Close Grip	Triceps: Close Grip

5)Statistical analyses:

The efficacy of the methods will be determined by:

1. a significant difference in term of pre and post treatment perception of well being between the groups
- 2.a significant difference in the lean/fat body mass ratio between the groups
3. a significant difference in BMI between the groups
4. a significant difference between the inflammatory parameters between the groups
5. a significant difference between the metabolic parameters between the groups

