
The data will be entered into an Excel spreadsheet and stored on the UIMCC hospital server. The patient data, including age, sex, race, underlying kidney disease, length of hospital stay, rejection episode, comorbidities, and medications will be coded and patient names will not be included in the datasheet.

The de-identified collected data will be entered into a SAS database. Initial descriptive analysis will include calculating means, standard deviations, ranges and frequencies. T-tests for continuous variables and Chi Square or Fischer exact tests of association for

categorical variables will be used to compare results of the study between the two groups for the efficacy parameters listed above. A P value<0.05 will be considered significant.

6) Benefits/risks

The main risk of this research is loss of confidentiality of medical information. Consent will be obtained for all patients. Master patient code list will be kept in a separate file accessible only by the primary investigator. A member of the transplant team will be available to answer any questions or discuss any concerns that patients may have.

The patient may experience mild anxiety or discomfort in providing information about their health and well-being. The patient may also have a potential to feel anxiety when being video recorded (if applicable).

Risks associated with the exercise program

The likely risks and discomforts expected in this study are those that largely involve being engaged in an exercise program after a prolonged period of inactivity. Such risks include: strains, sprains, and muscle soreness. Serious physical injury is considered unlikely given the screening for inclusion and physician approval. We will attempt to reduce risks of injury and harm by promoting gradual increases in exercise across time throughout the 3 month period and having exercise be instructed and supervised by trained professional fitness personnel.

Risks associated with the blood draw:

The risks associated with a blood draw include: mild pain, bleeding or bruising at the site of the draw. In general, any bruising should completely disappear within several days. There are minimal risks of fainting or hypotension (low blood pressure) during or after the blood draw.

Risks associated with the Maximal Aerobic Capacity Test (VO2 Test) and the 6 minute walk test include:

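### The arms are compared without sex or baseline in the model, which costs precision on the lean/fat ratio but does not bias the test

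*Combined protocol and SAP*

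**What the plan says.** The Setting paragraph of METHODS plans 225 patients "to achieve a goal of 180 patients in the GH study group and 45 patients in the control group". The Randomization paragraph says "All patients who meet the enrollment criteria will be randomized 4:1 to the GH group or the control group" and names no stratification factor.

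Section 5) Statistical analyses lists five efficacy criteria. The second is "a significant difference in the lean/fat body mass ratio between the groups". For these criteria the method is "T-tests for continuous variables and Chi Square or Fischer exact tests of association for" categorical variables, and "A P value<0.05 will be considered significant". No covariate model is described. The same section lists what is coded for each patient ("The patient data, including age, sex, race, underlying kidney disease" and further items), so sex will be in the dataset, but it has no stated part in the analysis.

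The table headed "GH Method: List of Strength/Resistance Exercises" gives one column for men and one for women. Strength is tested by Biodex at the knee extensors and flexors. The optional biopsy is taken from the biceps, once, with no pre-intervention sample.

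**The concern.** Lean/fat ratio, strength and aerobic capacity can be expected to differ in level between men and women. With only 45 controls and no stratification by sex, the arms may differ noticeably in sex mix by chance. An unadjusted comparison leaves the between-sex spread in the error term and carries any imbalance into the estimate. If nothing is prespecified, adjusting later for an imbalance that has been seen would be post hoc. At stake is the precision of a listed efficacy criterion, using a variable that is already collected.

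**Working it through.** **Inputs from the documents.** 180 GH and 45 control (METHODS, Setting); 4:1 with no stratum (Randomization); significance level 0.05 with sidedness not stated, taken here as two-sided (section 5).

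**Assumptions, not in the documents.** Male share p of 0.5 to 0.7; difference D between the sexes of 0.5 to 2 within-sex SD; within-sex SD set to 1.

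**The plan's own figure.** 225 × 4/5 = 180 and 225/5 = 45, so the split is exact. No effect size, SD or power is given, so 225 itself cannot be rebuilt.

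**Step 1: chance imbalance in sex.** SD of the difference in male share = √[p(1−p)(1/180 + 1/45)], where 1/180 + 1/45 = 0.02778.
- p = 0.5: √(0.25 × 0.02778) = 0.083; 95% range ±0.163; chance of more than 10 points 23%.
- p = 0.6: 0.082; ±0.160; 22%.
- p = 0.7: 0.076; ±0.150; 19%.

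**Step 2: effect on the estimate.** The shift is D times the imbalance. At p = 0.6 the 95% range is ±0.08, ±0.16 and ±0.32 within-sex SD for D = 0.5, 1 and 2. In total-SD units with half men, a 16-point imbalance gives 0.16/√1.25 = 0.14 for D = 1 and 0.24/√1.5625 = 0.19 for D = 1.5.

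**Step 3: is the test still valid?** In 40,000 simulated trials per setting (p = 0.6, no treatment effect), the unadjusted t-test rejected in 5.3%, 5.1% and 5.0% of trials for D = 0, 1 and 2. The mean difference was within 0.001 of zero each time. Imbalance in either direction is already reflected in the standard error.

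**Step 4: what precision is lost?** With sex in the model, SE = √0.02778 = 0.167, ignoring the small cost of one extra term. Without it, SE = √[(1 + p(1−p)D²) × 0.02778]. The effect detectable with 80% power when sex is in the model is (1.960 + 0.842) × 0.1667 = 0.467 SD. Power for that effect on 12-month values, with p = 0.6:

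| D | 1 + 0.24D² | SE without sex | Power without sex | Power with sex |
|---|---|---|---|---|
| 0.5 | 1.06 | 0.172 | 78% | 80% |
| 1 | 1.24 | 0.186 | 71% | 80% |
| 1.5 | 1.54 | 0.207 | 62% | 80% |
| 2 | 1.96 | 0.233 | 52% | 80% |

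**Step 5: which version of the outcome?** Criterion 1 refers to pre- and post-treatment values; criterion 2 does not say whether 12-month values or changes are compared. The table applies to 12-month values. A sex difference in level that is present at both visits cancels in a change score and is largely absorbed by a baseline covariate, so the further gain from sex is then much smaller.

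**Step 6: results by sex.** With half men, the arm-by-sex term has SE 2 × 0.1667 = 0.333, so 80% power needs 2.802 × 0.333 = 0.93 SD. For a biopsy subset of 30 against 8 (an assumed size; the documents give none), it needs 2.802 × 2 × √(1/30 + 1/8) = 2.2 SD.

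**The case against.** The strongest reply is that this is routine advice about efficiency. Randomisation protects the t-test, the sex effects above are assumed, and DEXA, Biodex and VO2max all have baseline measurements that remove most of the sex difference in level. Torque is also expressed per body weight. All of that stands, and it limits the point to precision. It does not remove it, because the plan adjusts for neither baseline nor sex.

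A reader might go further and infer that, because men and women have different exercise lists, the result depends on the sex mix of the 45 controls. The documents do not support this. Controls receive standard of care and are offered the GH regimen only after their final control visit, so the lists can act only through the GH arm. If the lists made the GH effect differ between the sexes by 0.2 or 0.5 SD, chance variation of about ±7 points in the male share of 180 GH patients would move the difference by only ±0.014 or ±0.036 SD (at 60% men). When an effect of this kind was simulated in the GH arm alone, control male shares of 0.3, 0.6 and 0.9 all gave a mean difference of 0.50.

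Nor can list entries be read as amounts of training. The bullets under Summary of GH Study Visits describe the list as a menu from which the week's exercises are drawn, with entries dropped or modified for the individual. The men's extra quadriceps line repeats leg extension, so the distinct quadriceps exercises are the same two. Hamstrings, also tested on the Biodex, have two entries in each column. Only biceps clearly differs, through the preacher curl on the men's list.

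Finally, the planned t-tests cover the five listed criteria. Biodex strength, VO2max and biopsy microRNA are not among them, so for these outcomes an analysis is being proposed where none is specified.

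**Conclusion.** The point holds as one of precision. The documents show unadjusted tests, sex recorded but unused, and no randomisation stratum. The chance difference in male share has an SD of about 8 points. Assuming 60% men and a 1 SD sex difference, leaving sex out raises the SE on 12-month values from 0.167 to 0.186 and lowers power from 80% to about 71%. Over sex differences of 0.5 to 2 SD, unadjusted power runs from 78% to 52%. Type I error stays near 5% and there is no bias on average. The size depends on assumed sex effects and sex mix, and is much smaller for change scores or with baseline in the model. The separate exercise lists are not the reason for the adjustment; they support at most an exploratory description by sex, which 45 controls cannot make confirmatory.

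**What to change.** In section 5, for the lean/fat ratio (criterion 2), replace the t-test with a linear model of the 12-month value on arm, baseline value and sex. If Biodex strength and VO2max are compared between the arms, specify the same model for them. For biopsy microRNA, which has no baseline sample, use arm and sex. Results for strength and biceps microRNA may also be described separately for men and women, labelled exploratory. The Randomization paragraph should say whether allocation is stratified and, if so, by what.

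The cost is a few lines of analysis text, settled before the outcome data are compared by arm. Sex and the baseline measurements are already collected, so no new data or visits are needed.

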- Control group: patient will be treated according to the standard of care for post-transplant recipients; control patients will be offered the opportunity to undergo the GH regimen for the 1 year after their final visit as a control patient. If the control patients chose to undergo the GH regimen, the extended follow up will be completed after 1 year from their final GH visit (totaling 4 years from the start of intervention).

Long-term follow-up

After the 12 month intervention period all patients will be followed for 2 additional years. Patients will be contacted by phone to assess current activity level, employment status, graft function and current weight. Patient's medical records will also be reviewed to confirm BMI and graft function. This will be done every 6 months.

A separate waiver of documentation of consent, for long-term follow up, is being requested for patients that have previously enrolled and completed the study (January 3, 2012 to July 28, 2014).

Parameters to analyze in all patients:

The PROMIS v.1.1 - Global Health short form will be administered to all patients at the time of enrollment, 6 months and at the end of the study (12 months). The PROMIS v.1.1 - Global Health short form will assesses health in general (i.e. overall health). The PROMIS Global Health short form is a 10-item instrument representing multiple domains (physical function, fatigue, pain, emotional distress, social health) as well as perceptions of general health that cut across domains. Global items allow respondents to weigh together different aspects of health to arrive at a “bottom-line” indicator of their health. Similar global health items have been found predictive of future health care utilization and mortality.

PROMIS 29 Profile v2.0 will be administered to all patients at the time of enrollment, 6 months and at the end of the study (12 months). The PROMIS 29 Prolife v2.0 is a short form containing four items from seven PROMIS domains (Depression, Anxiety, Physical Function, Pain Interference, Fatigue, Sleep Disturbance, and Ability to Participate in Social Roles and Activities) along with a single item on Pain Intensity.

Multiple studies have been conducted by the PROMIS Network validating these instruments. Studies are shown at: <http://www.nihpromis.org/science/validitystudies.aspx>

Body composition and strength

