BMI will be calculated at the time of enrollment, at 6 months, and at the end of the study (12 months). The most exact method to determine body fat and lean body mass is DEXA, a method that has been validated in patients with renal failure before and after transplantation [6,7]. Waist circumference as well as blood pressure will be measured for general health markers. Muscle strength will be measured using a Bidex machine. Exercise capacity will be measure with a 6 minute walk test and an accelerometer. Fitness level will be measure with a maximal aerobic capacity test (VO₂ max). These 7 tests will be done at baseline, 6, and 12 months.

Waist Circumference:

Waist circumference will be measured at the narrowest part of the torso (above the umbilicus and below xiphoid process) in the standing position using a tape measure. This will be completed at baseline, 6 months and 12 months post-intervention.

Blood Pressure:

Blood pressure will be measured in the supine position (lying on back) in a dimly lit room after resting for fifteen minutes. This will be completed at baseline, 6 months and 12 months post-intervention.

DEXA Scan: We will determine percent body fat via a whole body scan by dual energy x-ray absorptiometry (GE, IDX, Madison, WI), which will be operated and calibrated using the manufacturer's stated guidelines. The duration of the scan will be less than 10 min and the subject will be exposed to a radiation dose of ≤ 0.3 mrem based upon the manufacturer's specifications and calculations from Standford Dosimetry, LLC RADAR Medical Procedure Radiation Dose Calculator. This amount of research protocol radiation exposure is minimal given the estimated effective equivalent dose is below the 100 mrem per year, a limit set by the Nuclear Regulatory Commission for "general public" exposure.

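### Efficacy rests on five unranked criteria, each tested at P<0.05, with no primary endpoint, no any-or-all rule and no multiplicity control, so the plan as written does not hold a 5% error rate

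*Combined protocol and SAP*

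**What the plan says.** Section 5, Statistical analyses, contains the whole decision rule. It begins "The efficacy of the methods will be determined by" and numbers five items. The first is "a significant difference in term of pre and post treatment perception of well being between the groups". The second and third are the lean/fat body mass ratio and BMI. The fourth is "a significant difference between the inflammatory parameters between the groups", and the fifth has the same form for metabolic parameters. T-tests, or chi-square or Fisher tests for categorical data, are then applied "for the efficacy parameters listed above. A P value<0.05 will be considered significant".

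Three of the five items are families of measures:

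- **Well-being.** Criterion 1 names no instrument. Parameters to analyze in all patients gives PROMIS Global Health and PROMIS 29. The latter is "a short form containing four items from seven PROMIS domains" plus a pain-intensity item.
- **Inflammation.** Status of systemic inflammation lists ten circulating markers, introduced by 'such as', and M1/M2 macrophages.
- **Metabolism.** Metabolism and renal function changes lists glucose, HbA1c, four lipids and creatinine, taken during the study under standard of care.

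On timing, PROMIS and BMI are recorded at enrollment, 6 months and 12 months, and 12 months is called the end of the study. For the body-composition and fitness tests the text says "These 7 tests will be done at baseline, 6, and 12 months". The analysis section itself names no visit. The sample size of 225 (180 GH, 45 control) has no stated power or effect size, so it does not reveal a primary endpoint either.

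**The concern.** A rule under which efficacy is determined by significant differences has to say what pattern of results counts as success. Here that pattern is open in four ways: any or all criteria, one or several markers within a family, 6 or 12 months, and end value or change. Only criterion 1 refers to pre and post treatment. Each choice changes the false-positive rate, and the plan lets the choice be made after the results are known. The Long-term follow-up section says that some patients had already enrolled and completed the study between January 2012 and July 2014, so outcome data may exist before the rule is settled. At stake is whether a statement that the GH method works carries the error rate that P<0.05 implies.

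**Working it through.** **The plan's own figures.** There is no stated error rate or power to reproduce. Only the split can be checked: 180 + 45 = 225, and 180/45 = 4, the stated 4:1 allocation.

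**Counting the measures.**

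| Criterion | Main count | Lowest | Highest |
|---|---|---|---|
| Well-being | 1 Global + 7 domains + 1 pain item = 9 | 1 (one score) | 10 (Global as two scores) |
| Lean/fat ratio | 1 | 1 | 1 |
| BMI | 1 | 1 | 1 |
| Inflammatory | 10 markers + M1/M2 = 11 | 11 | 11 |
| Metabolic | 7 with creatinine | 6 without creatinine | 7 |
| Total | 29 | 20 | 30 |

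**Reading A: any one significant result is enough.** Assume no true effect on any measure, one visit and two-sided tests at 0.05. Under independence the chance of at least one significant result is 1 - 0.95^k:

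- k = 5: 22.6%
- k = 29: 77.4%

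Independence is unrealistic for 29 related markers. The documents give no correlations, so a range was assumed: one common correlation for the five single tests, and separate within-family and between-family correlations for the larger sets. Simulating correlated normal test statistics gives:

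| Set | Assumed correlation | Either direction | Favouring GH only |
|---|---|---|---|
| 5 single tests | 0.5 to 0 | 18-23% | 9-12% |
| 29 measures | 0.7/0.3 to 0.3/0.1 | 50-71% | 26-41% |
| 20 measures | 0.7/0.3 to 0.3/0.1 | 41-59% | 21-32% |

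Simulated t-tests with 180 v 45 patients agree. They gave 21.7% and 18.7% for five tests, and 65.0% and 49.4% for 29, at a common correlation of 0.3 and 0.5. Letting either the 6- or the 12-month result count would raise all of these.

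**Reading B: all five criteria must be met.**

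*One named test per criterion.* If at least one criterion has no true effect, P(all five significant) cannot exceed P(that one significant) = 0.05. When nothing works it is below 0.1% at correlations up to 0.5. The cost is power. At 80% per test, joint power is 0.8^5 = 33% if independent, 44% at correlation 0.3 and 51% at 0.5.

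*Any member satisfies its criterion.* When nothing works the rate is again tiny, at most 0.08% at the settings in the table. Now let four criteria have real effects and inflammation none. The chance that at least one of 11 null markers is significant is 1 - 0.95^11 = 43% under independence. Lean/fat ratio and BMI are single tests, so 80% power each gives 0.43 x 0.8 x 0.8 = 28%. The other two families are almost certain to supply a hit. At the three correlated settings, all five criteria are falsely met about 14-24% of the time. The figure is 22-37% if the other effects are strong. These count an inflammatory difference in either direction, so requiring a favourable one would lower them.

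**Effect of the fix.** Five tests at 0.05/5 = 0.01 give 1 - 0.99^5 = 4.9% if independent. The difference detectable with 80% power, in SD units and with all 225 patients analysed, is 0.47 at alpha 0.05, 0.56 at 0.05/4 = 0.0125 (the first Holm step over four tests) and 0.57 at 0.01.

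**The case against.** The rule never says that one result is enough. A numbered list can equally be read as requiring all five, or as five separate domain claims, under which lean/fat ratio and BMI are each a single 5% test per visit. This stands. A reader might infer that the plan carries a 50-71% risk of declaring a useless programme effective. The documents do not support that, because the figure needs the any-one reading, no true effect anywhere, assumed correlations and hits in either direction. The hypotheses are largely directional, and the favourable-only figures are lower.

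The opposite inference, that an all-five rule makes error negligible, is not supported either. It holds only when nothing works, or when each criterion is tied to one named test.

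Timing is also less open than the analysis section alone suggests. Treatment lasts 12 months, the Hypotheses section calls the 12-month DEXA measurement final, and 12 months is called the end of the study for PROMIS and BMI. Hypothesis 6 links well-being to PROMIS. These passages point to an intention, but none fixes the deciding test, and the metabolic labs have no stated visit.

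Finally, the study might be called exploratory, since the Benefits section speaks of contributing to understanding. That label does not fit a rule by which efficacy will be determined, or the stated aim of analysing effectiveness against standard of care.

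**Conclusion.** Wrong as written. The absence of a primary endpoint, a success rule and multiplicity control is a matter of text and needs no assumption. Its size depends on the reading. Under the any-one reading with no true effects, the risk at one visit exceeds 5% in every case examined. Counting only results in favour of GH, it runs from 9% (five tests, correlation 0.5) to 41% (29 measures, within/between correlation 0.3/0.1). Under the all-five reading it is held at 5% with one named test per criterion, at the price of 33-51% joint power. It is not held when any marker can satisfy its family.

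The correlations and the 80% power per measure are assumptions, and the count of 29 is a reconstruction with a range of 20 to 30. Nothing in the documents shows that outcome data by arm have been examined or that the rule was left open on purpose. The point is that the plan does not prevent a choice made after seeing results.

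**What to change.** Replace the five-item rule in section 5 with the following:

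- **Primary.** One endpoint at 12 months, chosen by the investigators (the DEXA lean/fat ratio is one candidate), stating whether the 12-month value or the change from baseline is tested. Conclude efficacy only if it favours the GH group at two-sided P<0.05.
- **Key secondaries.** One named measure at 12 months, with its favourable direction, for each of the other four criteria. Test these by Holm or in a fixed order, only if the primary succeeds.
- **Acceptable alternative.** No primary, but one named measure per criterion, each tested at 0.01.
- **Everything else.** Report other markers, PROMIS domains and 6-month results as supportive, with no efficacy claim.
- **Timing of the choice.** Because some patients have already completed the study, make these choices without sight of outcome data by arm and record this with a date. If such data have been seen, disclose it.

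The cost is an amendment and a dated statement. The downsides are real. No secondary claims are possible if the primary fails. Stricter thresholds raise the detectable difference from 0.47 SD to 0.56 SD (0.0125) or 0.57 SD (0.01) with 180 v 45 analysed. With an assumed 20% dropout (144 v 36) these become 0.53, 0.63 and 0.64 SD.
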